**3. Abstract:**

The purpose of this study is to test the efficacy of a patient-centered, tailored message intervention delivered via virtual technology for increasing colorectal cancer (CRC) screening within guidelines among racial/ethnic minority and rural patients. This protocol focuses on specific aim 2 of grant NCI 1RCA207689-01A1. In specific aim 2, patients (N=1,500) will be recruited via a secure, clinical data warehouse to complete a patient-randomized test of the efficacy of the intervention for promoting initial and repeat FIT screening. Patients identified as eligible will be contacted through MyChart and email to test a web-based, culturally-sensitive virtual human intervention for CRC screening. The web-application provides information to encourage CRC screening. Therefore, this study is a minimal risk study.

**4. Background:**

Most tailoring interventions rely on fully-tailored print messages. However, there is growing evidence that minimal tailoring may be as effective as full tailoring in some circumstances and that utilizing virtual human technology (VHT) to deliver tailored CRC screening messages may improve uptake. Interventions using VHT offer numerous advantages, including the capability to be customized to the preferences of the patient. As such, the use of virtual technology could help improve CRC screening by increasing cultural congruence, self-efficacy, and active patient engagement with screening information.

**The purpose of this study is to test the efficacy of a patient-centered, tailored message intervention for increasing CRC screening among racial/ethnic minorities and rural patients.** The intervention is based on theory and research in the area of message tailoring. The process of tailoring requires customizing intervention content to be personally relevant to the receiver. When messages are perceived as personally relevant, they are more likely to have a lasting effect on patient attitudes and screening behaviors. The intervention content will be tailored to patients on theoretical constructs causally associated with screening behavior change. Our hypothesis is that exposure to a minimally tailored CRC screening intervention delivered via VHT will lead to improved cognitive processing of the intervention and increased adherence with initial and repeated annual FIT screening completion as compared to a fully tailored, text-only intervention.

**5. Patient Eligibility and Recruitment**

We will recruit an ethnically diverse sample of eligible patients ( $N = 1,500$ , 750 men, 750 women, evenly distributed across White, African-American, Hispanic/Latino) to complete the intervention.

Eligibility criteria: patients must be between the ages of 45 and 73, able to read English or Spanish at least at eighth-grade level, have an email account or the ability to receive texts, and be out-of-guidelines for CRC screening within recommended guidelines (i.e., <10 years for colonoscopy, <3 years for Cologuard, <1 year for FIT). The primary outcome in the current study is CRC screening compliance. Compliance will be assessed by electronic medical record review (MRR) at 6, 12, and 18 months after enrolling in the study. Patients will be considered compliant if they a) complete a home stool test with a negative result only, b) complete a home stool test with a positive result AND undergo a completion screening colonoscopy, c) complete Cologuard only, or d) complete a colonoscopy only. We will also examine potential mediators of intervention effectiveness, such as exposure to the intervention, psychological processing of content (e.g., comprehension, perceived message quality), and online records of communication with a healthcare provider about screening.

Recruitment locations: Online at University of Florida Health, online through social media and online at community events (e.g., UFHealth Cancer Center (UFHCC) Office of Community Outreach and Engagement (COE), Community Clinical Navigation (CCN) and Mobile Outreach Clinic (MOC)).

Recruitment and retention methods: We will recruit current patients from UF Health Family Medicine and UF Health Internal Medicine electronically using the UF Integrated Data Repository (IDR) to locate eligible patients who have consented to be re-contacted for research purposes through the Consent2Share (C2S) program. Additionally, we will recruit patients outside of C2S. This is done to ensure that our study does not replicate existing health disparities hinging on patients' knowledge of the program. A variety of socioeconomic, cultural, and historical factors are thought to impact patients' willingness to participate in medical research and these factors often map along racial and ethnic lines. Because our study seeks to serve populations that are traditionally underserved medically, including racial and ethnic minorities, it is important that we reach all eligible participants, not only the subset that has enrolled in C2S. We will also recruit from UF Health Family and Internal Medicine outside of the IDR in collaboration with clinic managers, providers, and staff who have identified a patient as eligible for the study. Finally, we will recruit UF Health patients through Facebook (See Social Media Advertising Campaign).

We will be recruiting patients with active MyUFHealth accounts as well as patients who are not enrolled in MyUFHealth. Patients who have an active MyUFHealth account will be sent a message in MyUFHealth inviting them to participate in the study that contains both the English and Spanish versions of the recruitment email and informed consent; patients will select a language based on their preferences (Phase 1 English Recruitment and informed consent; Phase 1 Spanish Recruitment and informed consent). At the same time, we will also send them a physical mailer (Physical Mailer: enrolled in C2S and MyUFHealth or Physical Mailer: not enrolled in C2S, enrolled in MyUFHealth; English and Spanish versions) to inform them, and request their participation in a research study. This is done to increase the participation rates of those patients who do not frequently check their MyUFHealth account or associated e-mail account unless they are expecting a message.

We will recruit patients who do not have active MyUFHealth accounts using in-person recruitment methods developed in collaboration with clinic managers, providers, and staff in the UF Family Medicine and UF Internal Medicine clinics. We will invite patients to participate in the study via a physical mailer (Physical Mailer: C2S and non-C2S enrolled, not enrolled in MyChart; English and Spanish versions) and a message to their email account. The physical mailer will include information inviting them to sign up for MyUFHealth if they have not already done so. The flyer will contain information about how to enroll in MyUFHealth. When available, the flyer may also include dates and times for sessions where a study coordinator will be present at a clinic to assist patients in signing up for an account in-person. Participants who are not enrolled in MyUFHealth will be encouraged to sign up for a session to answer any questions they may have but walk-ins will also be allowed during the designated timeframe. Trained study staff will assist patients in enrolling in MyUFHealth and accessing the website application on their

cell phone (if desired). We will also provide laptop computers for patients who do not bring their own electronic device but still wish to enroll.

We will also recruit patients identified as eligible by clinic managers, providers, and staff outside of the MyUFHealth system using UF Qualtrics. Patient name, ID, language preference, and email, along with demographic information (race, gender) will be entered into a Qualtrics portal which will generate a customized link that is included within an emailed message based on the patient's language preference, inviting them to participate (Phase 1 English Recruitment and informed consent; Phase 1 Spanish Recruitment and informed consent).

In addition, study staff will participate in community health fairs and events hosted or attended by the UFHealth Cancer Centers Office of Community Outreach & Engagement (COE) where study information will be presented by study coordinators and interested patients will have the ability to speak with study staff and receive details on how to participate in the study. At community events, the COE team provides CRC screening via FIT tests, improving access to rural and high-socioeconomic vulnerability (SEV) communities in the 23 county UFHCC catchment area as well as as well as providing navigation services to all screened individuals to ensure results are received by PCPs as well as individuals completing the screening, and navigation for any needed follow-up care for positive screens (i.e., colonoscopy services). This approach ensures that all individuals receiving screening are guided through the continuum of cancer care and linked to accessible services, in the community where they reside and at low- or no-cost. The study team will present colorectal cancer education via the Meet ALEX website application to interested community members meeting eligibility criteria and refer those completing the study intervention to the COE team to obtain FIT tests if requested by the individual. The COE team will provide FIT testing to all individuals at no charge.

Outside the activities of the study, but in the concert with best practices for care coordination and according to standard practice community members or clinic patients that meet criteria for FIT testing are offered free test kits. The COE team provides all kit materials (including pre-paid mailer) and instructions on how to obtain the specimen. For all individuals completing FIT testing, from community events or clinic referrals, completed FIT tests are mailed to the COE team for on-campus processing at UF laboratory facilities (GCRC). Results are shared with referring providers and results are provided to patients, by the COE team, in letter form as well as a phone call. All communications are documented and shared with clinical teams for integration into the electronic medical records (EMRs).

We will also recruit patients through Facebook (See Social Media Advertising Campaign). Ads will be posted through the official UF Studies Facebook page ([www.facebook.com/ufstudies](http://www.facebook.com/ufstudies)) with assistance from the CTSI Recruitment Center, and UFHCC COE. The ads will link to the study Qualtrics portal previously described.

Approximately one week after initial contact, the patients that have not enrolled will receive an email message reminding them about the study (English and Spanish - Phase 1 Enrollment Reminder Script: E-mail). Patients who are enrolled in MyChart, either through the study or otherwise, will receive additional weekly reminders about completing the study (English and Spanish - Phase 1 Enrollment Reminder Script: Phone/Voicemail and Phase 1 Enrollment Reminder Script: Text message).

In light of COVID-19, staff were added to conduct quality control calls and add video conferencing to replace face-to-face assistance to participants. Staff in addition to community health workers (CHWs) on the research team will contact participants for quality control. Communication activities have transitioned to Zoom-PHI video conference calls for assistance with technical issues enrolling in the intervention.

Intervention: Patients will interact with an online educational application which delivers an educational message about FIT screening (Phase 1). They will be randomly assigned to receive a standard, text-based tailored message or a tailored message delivered by a virtual human. The message itself is

comprised of a brief core message about the importance of screening as well as up to 10 additional constructs which may influence decision to screen: message source, perceived severity, risk probability, perceived susceptibility, framing, perceived benefits, response efficacy, perceived barriers, narrative persuasion, and self-efficacy. In both conditions, the information is presented to patients as coming from a “virtual healthcare assistant” in the form of either VHT or a still image. Participants will be randomly assigned to see either a demographically-concordant or demographically-discordant virtual healthcare assistant. Patients seeing a concordant assistant will be matched based on race and gender. Participants seeing a discordant assistant will be mismatched on race or gender or both. Participants whose preferred language as listed in Epic is Spanish, or who were recruited through Qualtrics and self-selected Spanish as their preferred language, will receive a Spanish-language version of the intervention.

In both the text-based and virtual human versions of the intervention, some patients will randomly see constructs featuring interactions with the virtual human. These interactive segments ask patients information about their behaviors related to CRC and screening, such as the frequency with which they eat red meat and potential barriers to screening they face. These questions will be used to randomly deliver either a tailored response to the patient’s feedback or a generic, non-tailored response.

Upon completion of the interaction with the app, patients will complete a short (i.e., 20 minute) algorithmic questionnaire that utilizes survey responses to assess attitudes and screening behaviors associated with CRC. Participants recruited through the IDR and UF Qualtrics will complete the questionnaire using web-enabled devices such as computers or tablets. Participants in phase 1 will be remunerated \$30.00 for interacting with the app and completing the subsequent questionnaire.

After completion of the interaction patients will also complete a brief questionnaire (Post-intervention screener) to assess interest in screening, their screening status, and CRC risk. For patients who are unsure of their screening status or risk-level, project staff will conduct medical record review and/or consult with the PCP. Patients at low/average risk will be asked whether they would like to request a FIT test. Patients at high-risk will be asked whether they would like to speak with their primary care physician about colonoscopy. For all patients regardless of risk-level who click “Yes,” the system will send a request to their primary care physician to consult with the patient. If a FIT order is approved, we will then send the appropriate FIT kit to the participant at the requested address. Participants will be reminded to complete and return their kits to their clinic or lab at 2 weeks (English and Spanish - FIT Kit Reminder A Script; e-mail), 4 weeks (English and Spanish - FIT Kit Reminder B Script; text message), and 6 weeks (English and Spanish - FIT Kit Reminder C Script; phone message) after being mailed the kit.

For patients accessing the intervention through UF Qualtrics, screening status and risk will again be assessed with a similar procedure. For the patient FIT request message, an additional item will be included on the questionnaire asking them if they would like to request a FIT test. For patients choosing “Yes,” physical address as well as email will be collected and stored in UF Qualtrics.

After questionnaire completion patients will be directed to a compensation survey where name, physical address, and email are collected for the purpose of distributing study compensation.

One month after the initial invitation and reminders (Phase 2), participants who have not completed Phase 1 of the intervention or did not request screening after completing Phase 1 of the intervention, will be re-contacted through MyUFHealth or email and re-invited to the study. Participants will be remunerated \$10.00 for completing the intervention at Phase 2.

In Phase 3, participants who respond to the intervention will receive an invitation in MyUFHealth or email 12 months after the date of their initial recruitment inviting them to click on a link to receive a booster message encouraging regular, repeated screening and offering them the opportunity to request their annual FIT kit from their provider. Participants will then complete 5-10 short questions relevant to their

experience with FIT (e.g., “How easy was it for you to follow the instructions that came with your FIT test?”) and any pertinent changes to their health history (e.g., “Has anyone in your family been diagnosed with colorectal cancer in the past year?”). Participants will be remunerated \$5.00 for completing the booster questionnaire.

In addition to the post intervention test, we will monitor Epic for participants' screening compliance (to determine whether they have engaged in behavioral change), whether they make appointments with their doctors (to establish whether they engage in informed decision-making with their healthcare provider) and whether they request repeat testing the following year (to track long-term behavioral change). We will also track whether people were diagnosed with CRC to see whether the intervention has significant impacts on detection of CRC rates among participants.

To ensure that our technology systems are functioning as expected and that patients have received their mailed FIT kits, we will conduct quality control calls with patients who do not finish the intervention, who do not respond to recruitment messages, or who do not have screening results entered into their MR. A research coordinator or community health worker (CHW) will call patients and ask if they encountered any technical difficulties in using the intervention, or if they received their FIT kit and encountered any difficulty using it. If the patient encountered technical problems, we will gather relevant details (such as web browser used) and pass this information along to our technology team. This will allow them to troubleshoot problems and increase completion rates. If the patient encountered problems with screening, we will again gather relevant details and provide the needed guidance/support.

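### The primary compliance rule counts a positive Cologuard without colonoscopy as compliant but a positive FIT without colonoscopy as non-compliant

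*Combined protocol and SAP*

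**What the plan says.** Section 5 (Patient Eligibility and Recruitment) states: "The primary outcome in the current study is CRC screening compliance". It is scored by medical record review at 6, 12 and 18 months after enrolment, and any one of four routes is enough:

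- Route (a): "a) complete a home stool test with a negative result only".
- Route (b), running on into (c): "b) complete a home stool test with a positive result AND undergo a completion screening colonoscopy, c) complete Cologuard only".
- Routes (c) and (d) together: "c) complete Cologuard only, or d) complete a colonoscopy only".

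The term home stool test is not defined. The eligibility sentence in the same section names Cologuard and FIT as separate tests with different look-back periods: "<3 years for Cologuard, <1 year for FIT". The test that the study offers is FIT: "Patients at low/average risk will be asked whether they would like to request a FIT test". Section 6 (Study Design) says how compliance is ascertained, and its Sample Size Analysis lists compliance as a primary endpoint. Neither puts a result condition on route (c).

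**The concern.** Routes (a) and (b) together make a stool test count only when the screening episode is closed, either by a negative result or by a colonoscopy after a positive one. Route (c) drops that requirement for Cologuard. Two patients in the same position, each with a positive test and no colonoscopy, get opposite scores on the primary endpoint according to which test they used.

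The scoring dates make this wider than patients who never follow up. If the colonoscopy after a positive Cologuard falls after the 6-month review, the patient already counts at 6 months. A FIT patient with the same dates does not.

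At stake are what the compliance rate means and, to a small extent, its level.

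**Working it through.** The plan gives no figure on this point to reproduce. The sample-size numbers (1,000 evaluable, 33% attrition, 1,500 enrolled; 1,000 / 0.67 = 1,493) agree with each other, and the point does not rest on them.

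**Step 1: apply the written rule to each case.** Take FIT as a home stool test and the four routes as alternatives.

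| Test | Result | Colonoscopy | Score | Route |
|---|---|---|---|---|
| FIT | negative | no | compliant | a |
| FIT | positive | yes | compliant | b |
| FIT | positive | no | **not compliant** | none |
| Cologuard | negative | no | compliant | c |
| Cologuard | positive | yes | compliant | c |
| Cologuard | positive | no | **compliant** | c |

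Only the case of a positive result without colonoscopy is scored differently for the two tests.

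**Step 2: try both readings of the undefined term.** If home stool test excludes Cologuard, the asymmetry is explicit. If it includes Cologuard, a positive Cologuard without colonoscopy fails (a) and (b) but still passes (c), because one route suffices. The score is the same under both readings.

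**Step 3: size.** The share of compliers whose score would change is

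s = (Cologuard share of compliers) × (positive) × (no follow-up colonoscopy).

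The documents give none of the three inputs. Assumed ranges are 10–30%, 10–20% and 20–50%.

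- Low: 0.10 × 0.10 × 0.20 = 0.002, or 0.2%.
- High: 0.30 × 0.20 × 0.50 = 0.030, or 3.0%.
- Per 500 compliers: 500 × 0.002 = 1 and 500 × 0.030 = 15.

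**Step 4: effect on the rate.** A compliance rate R under the written rule becomes R × (1 − s). With R assumed to be 50% (500 of the 1,000 evaluable patients), the rate falls to 0.50 × 0.998 = 49.9% at the low end and 0.50 × 0.97 = 48.5% at the high end, a drop of 0.1 to 1.5 percentage points.

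**Step 5: effect on the comparison if s is equal in both arms.** The difference between arms is multiplied by (1 − s). At the upper value, a difference equal to the plan's margin of 0.075 becomes 0.075 × 0.97 = 0.073. The contrast hardly moves.

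**The case against.** A reader might infer that the rule biases the comparison between arms, because tests prompted by the study face the stricter condition. The documents do not support that. Sections 4 and 5 describe arms that differ in how the message is delivered. Both receive education about FIT, and the FIT offer afterwards does not depend on arm. No arm promotes Cologuard or omits FIT. For scale, take wider assumed ranges with all participants as the base: 20% Cologuard use, 20% positive and 80% without colonoscopy. The product is 0.20 × 0.20 × 0.80 = 3.2%, or 0.032 / 0.075 = 43% of the margin. It would become a between-arm difference only if every such case fell in one arm, and nothing suggests that.

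A reader might also take the community-event text in Section 5, "navigation for any needed follow-up care for positive screens (i.e., colonoscopy services", as proof that the trial regards any positive test as unfinished. That text concerns FIT screening by the outreach team. It does not mention Cologuard or define the endpoint.

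Three further objections have some force:

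- **Intent.** The wording of (c) may be shorthand for a Cologuard that needed no follow-up. That is plausible, but (a) states the negative result and (c) does not, so a record reviewer following the text has no basis for adding it.
- **Which route is out of line.** The eligibility sentence judges both tests by interval alone, without regard to result, and (c) resembles that. The sponsor could therefore justify a different reconciliation. But the eligibility sentence treats the two tests alike, so it gives no reason to score them differently.
- **Size.** It rests wholly on assumed inputs and may be negligible. This stands.

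**Conclusion.** The concern holds as an internal inconsistency in the primary-endpoint rule. It follows from the wording of the four routes and needs no assumption about rates. Its size does: 0.2% to 3.0% of compliers under the assumed inputs, or 0.1 to 1.5 percentage points on an assumed 50% compliance rate. The direction is towards a higher absolute compliance rate than a uniform result-based rule would give. Bias between arms would need unresolved positive Cologuard tests to be unevenly distributed, and the documents do not show this. The point is worth correcting because the rule is primary and the correction is cheap, not because it threatens the trial's conclusion.

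**What to change.** Before compliance is scored, and without reference to results by arm:

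- Define home stool test and say whether it includes Cologuard.
- Reconcile routes (b) and (c) and use one result-based rule for all home tests. Wording consistent with (a) and (b): Cologuard counts if negative, or if positive with a completed colonoscopy.
- Apply the rule in the same way at the 6-, 12- and 18-month reviews, and state how a Cologuard with no result on file is scored. The documents do not say that results of tests obtained outside the study reach the reviewed record.
- If the sponsor prefers to keep the two tests on different rules, give the reason in the protocol.

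This alters outcome scoring only and leaves patient care untouched. The cost is a small wording change, one more field on the record-review form, and a slightly lower compliance rate.

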## **7. Data Management:**

We worked with representatives of UF Health Network and MyUFHealth to situate the intervention within MyUFHealth. The interaction itself will be hosted using Virtual People Factory (VPF), a web platform which hosts virtual human interactions. We will use Amazon Web Service (AWS) to store data from the interaction as well as host the virtual human webpage. For our design, human subjects need to be randomized to see either a demographically-matched VH or a demographically-dissimilar VH. They will also see either a video recruiting message a UF Health provider or a written recruiting message with a photo of the provider.

Representatives from IDR will set up weekly pulls of eligible patients and will upload lists of these patients and their contact information onto a secure, password-protected server housed in the University of Florida's Health Sciences Center. Each human subject will be sent a message in MyUFHealth inviting them to click on a link. We will use script to append the subject's MyUFHealth ID number to the end of the link to create a customized URL. For patients initially recruited outside of MyUFHealth through UF Qualtrics, after entering name, patient ID, email, and demographics a unique ID will be created and appended to a customized URL link. Clicking on the URL takes the subject to the secure server housed in the University of Florida's Health Sciences Center. The secure server runs a program replacing the MyUFHealth ID number with a random Participant ID number before redirecting the subject to the virtual human app. The program records both numbers in a key document which is updated daily and uploaded to the secure, password-protected server.

In this way, no PHI leaves the secure UF Health network, but we can still record the subjects' interactions within the intervention and match their answers up with the survey data collected from MyChart. The participant ID number on its own contains no PHI. The only way the random participant ID number on its own could be used to identify human subject and access PHI would be to breach the security of the UF Health Sciences Center server and MyUFHealth. No PHI leaves the UF system. No PHI is transmitted to VPF or AWS. All data will be monitored systematically to identify any security weaknesses, and data files will be backed up to protect against data corruption.

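### MyUFHealth patients choose English or Spanish at invitation and consent, but the app language follows the Epic field, so a patient can be assigned a language they did not choose

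*Combined protocol and SAP*

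**What the plan says.** Three parts of Section 5 (Patient Eligibility and Recruitment) bear on language.

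- **Eligibility.** A patient must be "able to read English or Spanish at least at eighth-grade level". Either language is enough.
- **MyUFHealth recruitment.** The message sent to account holders "contains both the English and Spanish versions of the recruitment email and informed consent", and "patients will select a language based on their preferences".
- **Intervention.** The Spanish version of the app goes to "Participants whose preferred language as listed in Epic is Spanish, or who were recruited through Qualtrics and self-selected Spanish as their preferred language". The paragraph does not say what everyone else receives; English is implied.

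For patients identified by clinic staff, Section 5 provides that "Patient name, ID, language preference, and email, along with demographic information (race, gender) will be entered into a Qualtrics portal", and the emailed invitation follows that language. Facebook advertisements lead to the same portal.

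Section 7 (Data Management) describes the MyUFHealth link. A script appends the "MyUFHealth ID number to the end of the link to create a customized URL", and a server program then replaces that number with a random participant number before sending the patient on to the app. No language value is mentioned at either step.

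**The concern.** On the MyUFHealth route two sources of language are in play: what the patient selects and what Epic holds. The plan uses the first for invitation and consent and the second for the app. It does not say that the selection overrides or updates Epic, or that the patient can switch language inside the app.

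The intervention is a message that has to be read or heard and understood. Section 5 names comprehension and perceived message quality as mediators, and the sample size part of Section 6 lists mediators among the primary endpoints. A message in a language the patient did not choose is a weaker version of the intervention. For a patient who reads only the other language, it may be no intervention at all. The burden would fall mainly on Hispanic/Latino participants, one of the groups the trial is meant to serve.

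**Working it through.** The plan gives no figure on this point, so the main check is a comparison of the two rules.

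**Step 1. Apply the Intervention rule to each combination for a MyUFHealth patient.**

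| Epic language | Patient's selection | App language under the rule | Match? |
|---|---|---|---|
| Spanish | Spanish | Spanish | Yes |
| Not Spanish | English | English (implied) | Yes |
| Spanish | English | Spanish | No |
| Not Spanish, or blank | Spanish | English (implied) | No |

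Two of the four combinations give a language the patient did not choose. The last row matters most. That patient meets neither condition for the Spanish app, yet is eligible when Spanish is the only language they read.

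**Step 2. Look for a correction downstream.** Section 7 carries only an identifier through the link and redirect. The quality control calls in Section 5 ask about technical difficulties and FIT kits; language is not among the stated questions. No described step changes the result in Step 1.

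**Step 3. Illustrate the size.** Inputs:

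- Hispanic/Latino target: 1,500 / 3 = 500, from the even split over three groups in Section 5.
- p, the share of these recruited through MyUFHealth: not in the documents. Assumed 0.5 for illustration.
- d, the share of those whose Epic field differs from their selection: not in the documents. Assumed 0.05 to 0.20.

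Number affected = 500 × p × d.

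- p = 0.5, d = 0.05: 500 × 0.5 × 0.05 = 12.5, about 13.
- p = 0.5, d = 0.20: 500 × 0.5 × 0.20 = 50.
- p = 1, as the outer limit: 25 to 100. This requires that no Hispanic/Latino participant comes through Qualtrics.

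**Step 4. Bound the dilution.** Suppose the mismatched message has no effect at all and the true effect is the same in all three groups. The effect is then diluted by the affected share. With p = 0.5:

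- Hispanic/Latino group: 12.5/500 = 2.5% to 50/500 = 10%.
- Whole sample: 12.5/1,500 = 0.8% to 50/1,500 = 3.3%.

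For the assumed p and d these are ceilings, since any retained effect lowers them.

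**The case against.** The best case for the plan runs as follows. The recruitment text says that patients pick a language, but not that the pick is recorded; they may simply read one of two versions supplied together. Epic's field is itself a recorded language preference. An undocumented hand-over of the choice to the app, or a language switch inside it, cannot be excluded. Staff also call patients who do not finish, video help is available (Section 5), and Section 8 gives patients a telephone number.

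Part of this stands. The documents do not show that wrong-language delivery has occurred or how common it would be, and the English default is implied. A bilingual patient shown the other language need not lose the whole effect.

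The rest does not remove the point. The Intervention paragraph is not merely silent: it states which patients receive Spanish and limits self-selection to one route. If the app in fact follows the patient's choice, that paragraph is wrong and should say so. The calls, video help and telephone number may bring a stranded patient to notice, but none of them is described as setting or correcting the app language.

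**Conclusion.** The point holds as an inconsistency between two stated rules in Section 5, limited to patients recruited through MyUFHealth. It needs no numerical assumption. Its size does: about 13-50 patients if half of the 500 come by that route and 5-20% are discordant, both assumed. The documents supply neither share. The expected consequence is modest dilution of message effect and comprehension, alike in both arms because language is not a randomized factor. This is worth correcting but does not threaten the trial.

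A reader might infer more, and the documents do not support it:

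- **That 25-100 patients are affected, with 1.7-6.7% overall dilution** (25/1,500 to 100/1,500). This puts all 500 on the MyUFHealth route and assumes total loss of effect. Section 5 plans Qualtrics recruitment through clinics and Facebook, and those patients may self-select.
- **That recruitment route is confounded with quality of delivery.** Route is neither randomized nor a planned comparison in Section 6, so no planned contrast is confounded.
- **That the questionnaire, reminders and booster also follow Epic.** No section says so; reminder scripts exist in both languages.

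**What to change.** Replace the language rule in the Intervention paragraph of Section 5 with one rule for all routes: the app is shown in the language the patient selects at invitation or consent, and the Epic field is only the default when no choice is made. This brings MyUFHealth recruits under the principle already applied to Qualtrics recruits.

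To make it work, the choice has to be captured. A separate link in each language version of the MyUFHealth message would do this. Section 7 should then state that the language value is carried through the step that replaces the ID number.

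Record both the selected and the Epic language for each participant, so that the discordance rate can be reported instead of assumed.

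The cost is a small programming change to the link and the redirect, an additional language record, and short edits to Sections 5 and 7.
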